5. GENERAL METHODOLOGY AND CONVENTIONS

Final analysis will be performed after study participant data set release following last participant last visit.

5.1. Hypotheses and Decision Rules

The alternative hypothesis of bioequivalence ($H1: q_L \leq m_T - m_R \leq q_U$), and the null hypothesis of inequivalence ($H0: m_T - m_R < q_L$ or $m_T - m_R > q_U$) can be expressed as the following 2 separate one-sided hypotheses:

$HoA: m_T - m_R < q_L$

$H1A: q_L \leq m_T - m_R$

$HoB: m_T - m_R > q_U$

$H1B: m_T - m_R \leq q_U$

where m_T and m_R represent the average bioavailability on a log scale for the Test and Reference products respectively and $[q_L, q_U]$ defines the bioequivalence range.

Bioequivalence of the Test treatment to Reference treatment will be concluded if the 90% confidence intervals for the ratios of adjusted geometric means for tafamidis AUC_{inf} (if data permit, otherwise AUC_{last}) and C_{max} fall entirely within the acceptance region of (80%, 125%).

5.2. General Methods

5.2.1. Analyses for Binary/Categorical Endpoints

For binary or categorical variables, number of participants, numbers and percentages of participants meeting the categorical criteria will be presented in accordance with the Clinical Data Interchange Standards Consortium and Pfizer Standards (CaPS).

5.2.2. Analyses for Continuous Endpoints

For continuous variables, the data will be summarized using the number of participants, mean, median, standard deviation (SD), minimum, and maximum in accordance with the CaPS. For appropriate PK parameters, geometric mean and geometric coefficient of variation (%CV) will also be summarized.

5.3. Methods to Manage Missing Data

5.3.1. Pharmacokinetic Data

Methods to handle missing PK data are described below.

Concentrations Below the Limit of Quantification:

In all data presentations (except listings), concentrations below the limit of quantification (BLQ) will be set to zero. (In listings BLQ values will be reported as “<LLQ”, where LLQ will be replaced with the value for the lower limit of quantification.).

Deviations, Missing Concentrations and Anomalous Values:

In summary tables and plots of median profiles, statistics will be calculated having set concentrations to missing if 1 of the following cases is true:

1. A concentration has been collected as ND (ie, not done) or NS (ie, no sample).
2. A deviation in sampling time is of sufficient concern or a concentration has been flagged anomalous by the pharmacokineticist.

Note that summary statistics will not be presented at a particular time point if more than 50% of the data are missing.

An anomalous concentration value is one that, after verification of bioanalytical validity, is grossly inconsistent with other concentration data from the same individual or from other

[figure not shown]
participants. For example, a BLQ concentration that is between quantifiable values from the same dose is considered as anomalous. Anomalous concentration values may be excluded from PK analysis at the discretion of the PK analyst.

PK Parameters:

Actual PK sampling times will be used in the derivation of PK parameters. If a PK parameter cannot be derived from a participant's concentration data, the parameter will be coded as NC (ie, not calculated). (Note that NC values will not be generated beyond the day that a participant discontinues).

In summary tables, statistics will not be presented for a particular treatment group if more than 50% of the data are NC. For statistical analyses, PK parameters coded as NC will also be set to missing.

CCI

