9.3. Statistical Analyses

The SAP will be developed and finalized before any analyses are performed and will describe the analyses and procedures for accounting for missing, unused, and spurious data. This section is a summary of the planned statistical analyses of the primary and secondary endpoints.

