9.5. Sample Size Determination

The sample size of 22 participants (11 participants per sequence in the fasted arms) to ensure a minimum of 18 PK evaluable participants for this 3-way crossover will provide 97% power that the 90% confidence interval for the ratio of Test to Reference for AUC_{inf} will lie within the acceptance region of (80%, 125%) and 89% power that 90% confidence interval for the ratio of Test to Reference treatment for C_{max} will lie within the acceptance region of (80%, 125%). Consequently, this study has approximately 86% power overall to demonstrate bioequivalence of the Test treatment to the Reference treatment [ie, equivalence in both AUC_{inf} and C_{max}]. This estimate is based on the assumption that the true ratio between Test and Reference treatments for both AUC_{inf} and C_{max} is 0.9.

The power calculations assumed the estimates of within participant standard deviations of 0.098 and 0.119 for $\log_e AUC_{inf}$ and $\log_e C_{max}$, respectively, obtained as an average from studies B3461030, B3461044 and B3461095.

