4. ANALYSIS SETS (POPULATIONS FOR ANALYSIS)

Data for all participants will be assessed to determine if participants meet the criteria for inclusion in each analysis population prior to releasing the database and classifications will be documented per standard operating procedures.

Participant Analysis Set	Description
Enrolled	“Enrolled” means a participant’s, or their legally authorized representative’s, agreement to participate in a clinical study following completion of the informed consent process and randomization/assignment to study intervention. A participant will be considered enrolled if the informed consent is not withdrawn prior to participating in any study activity after screening. Potential participants who are screened for the purpose of determining eligibility for the study, but do not participate in the study, are not considered enrolled, unless otherwise specified by the protocol.
Full analysis set	Example: All participants randomly assigned to study intervention and who take at least 1 dose of study intervention.
Safety analysis set	All participants randomly assigned to study intervention and who take at least 1 dose of study intervention. Participants will be analyzed according to the product they actually received.
PK Concentration	The PK concentration population is defined as all participants who receive at least 1 dose of tafamidis and who have at least 1 measurable concentration of tafamidis.
CCI	

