7. INTERIM ANALYSES

No formal interim analysis will be conducted for this study. As this is an open-label study, the sponsor may conduct unblinded reviews of the data during the course of the study for the purpose of safety assessment, facilitating PK modeling, and/or supporting clinical development.

Final analysis will follow the official database release. As this will be an open-label study, there is no formal unblinding of the randomization code.

APPENDICES

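### Does the SAP need a fixed rule on whether a concentration flagged as anomalous enters the Cmax that decides bioequivalence?

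*SAP*

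**What the plan says.** SAP 5.3.1 treats a flagged concentration in two places.

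- **Summary tables and median profile plots:** "statistics will be calculated having set concentrations to missing if 1 of the following cases is true", and one of the cases is that "a concentration has been flagged anomalous by the pharmacokineticist". This is mandatory.
- **Derivation of AUC and Cmax:** "Anomalous concentration values may be excluded from PK analysis at the discretion of the PK analyst". This is optional.

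The section limits what may be flagged: "An anomalous concentration value is one that, after verification of bioanalytical validity, is grossly inconsistent with other concentration data", from the same person or from others. Its one example is a value below the quantification limit lying between quantifiable values.

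Three other places bear on the point. Protocol 9.3 says that the SAP "will describe the analyses and procedures for accounting for missing, unused, and spurious data". SAP 4 has analysis-set membership assessed "prior to releasing the database and classifications will be documented per standard operating procedures". SAP 6.1 has model residuals inspected for outliers, the effect of any outliers on the conclusions investigated (analyses without them are among the options), and any departure from the planned analysis justified in the study report.

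**The concern.** The two sentences in 5.3.1 allow the descriptive tables and the bioequivalence model to rest on different data. The definition says what may be flagged. It does not say whether a flagged value then stays in Cmax. The visible text sets no deadline for that choice relative to the first Test/Reference ratio, and it does not ask for results both ways. SAP 4 does set a deadline for analysis sets. The study is open-label, sponsor staff know the treatments (protocol 6.4.3), and SAP 7 says the "sponsor may conduct unblinded reviews of the data during the course of the study for the purpose of safety assessment, facilitating PK modeling" among other reasons.

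Cmax is the highest observed concentration, so one gross value can set it for a participant and period. If the verdict on a co-primary endpoint could turn on an unrecorded choice, the error rate of the bioequivalence test would be open to question.

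**Working it through.** **Inputs.** From protocol 9.5: 18 evaluable of 22 enrolled, two equal sequences, within-participant SD 0.119 for log Cmax, and power "based on the assumption that the true ratio between Test and Reference treatments" is 0.9. From SAP 6.1: the 90% CI must lie within 80–125%. Assumed, because the documents give no figure: one participant's Cmax in one period is inflated 1.5-, 2- or 3-fold by a single concentration, and excluding that concentration restores the ordinary Cmax. The second assumption is reasonable with 16 samples per period. In assumed one-compartment profiles (half-life 30–70 h) the next-highest sample is 98.6–99.9% of the peak.

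**The plan's own figure.** Two one-sided t-tests, df = 18 − 2 = 16, SE = 0.119 × √(2/18) = 0.0397. The distance to the lower limit is ln 0.9 − ln 0.8 = 0.1178. Exact power is 88.4%, against 89% stated. The excluded case is therefore the planned case.

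**One inflated Reference value.** A 2-fold value shifts the log ratio by −ln 2/18 = −0.0385, a factor of 2^(−1/18) = 0.962. The mean CI half-width rises from 0.068 to 0.095. A typical lower limit is then:

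- excluded: exp(−0.1054 − 0.0682) = 0.841, a pass;
- kept: exp(−0.1054 − 0.0385 − 0.0954) = 0.787, a fail.

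Chance of meeting the Cmax criterion at true ratio 0.9 (200,000 simulated trials per scenario):

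| Inflation of one Reference Cmax | n=18 excluded | n=18 kept | verdict differs | n=22 excluded | n=22 kept | verdict differs |
|---|---|---|---|---|---|---|
| 1.5-fold | 88% | 66% | 23% | 94% | 80% | 14% |
| 2-fold | 88% | 35% | 53% | 94% | 55% | 39% |
| 3-fold | 88% | 5% | 83% | 94% | 16% | 77% |

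The 2-fold differences fall to 18% (n=18) and 6% (n=22) at a true ratio of 0.95, and to 2% and 0.2% at 1.0. A 2-fold Test value at ratio 0.9 changes the verdict in only about 5% of trials (n=18). AUC hardly moves: at most 1.1% in the ratio at n=18.

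**Does discretion raise the false-positive rate?** Take true ratio 0.80, n=18 and a 2-fold value, and let the analyst choose whichever option passes.

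| Value | Always exclude | Always keep | Choose the passing result |
|---|---|---|---|
| Reference | 5.0% | 0.1% | 5.0% |
| Test | 5.0% | 8.9% | 9.2% |

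In the Reference case choosing gains nothing over a fixed rule of exclusion, because keeping the value only makes passing harder. In the Test case 8.9 − 5.0 = 3.9 points come from keeping the value, and 9.2 − 8.9 = 0.3 points from being free to choose.

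**Would a kept value be noticed?** With n=18 and ratio 0.9, a kept 2-fold value is the largest residual in 94% of trials and exceeds 2.5 studentized units in 77%. For a 3-fold value both are about 100%. For a 1.5-fold value they are 56% and 25%, but a value that mild may not count as grossly inconsistent.

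**Would an excluded value be noticed?** The set-to-missing rule names only summary tables and median plots. Protocol 9.3.2 (PK methods) has concentrations listed and individual profiles plotted, and the synopsis adds individual Cmax plotted by treatment. A listed concentration above that participant's plotted Cmax would show the exclusion.

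**The case for a change.** The strongest reply is that SAP 6.1 sees only what enters the model. A concentration removed before Cmax is derived leaves no residual, so the choice with least oversight is the one that check cannot reach. Listings let a careful reader find the value, but nothing in the visible text makes the report state the exclusion or its effect. The BLQ example does not help with a high value, which is the kind that sets Cmax. A written rule would be cheap.

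All of that is accurate, and it is also true that a fixed rule of exclusion would avoid the 9% in the Test case. But the unseen route, exclusion, is the one that holds the false-positive rate at 5.0% when the value really is spurious. The route that inflates it, keeping a high Test value, is the one SAP 6.1 examines. Asking for a single rule without saying which would not by itself remove the 9%, since a rule of always keeping carries nearly all of it. Reporting with and without the value partly repeats SAP 6.1. Protocol 9.3 is met: the SAP gives verification, a definition, an example, flagging and possible exclusion. The unblinded-review wording adds little, because PK modelling is not the bioequivalence comparison and the documents do not say that the PK analyst is sponsor staff.

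**Conclusion.** The two sentences do differ, and the visible text sets neither the timing of an exclusion nor a requirement to report its effect. That is missing detail, not a flaw in the analysis. The discretion applies only to values already verified and judged grossly inconsistent. An analyst who treats such a value in the parameters as the summaries treat it recovers the planned 88–89% power and the nominal 5% error rate.

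The large verdict differences (23%, 53% and 83% at n=18) show how much a gross value matters. They do not measure harm from discretion, which adds 0.0 points to the false-positive rate for a 2-fold Reference value and 0.3 points for a 2-fold Test value. The power figures depend on a true ratio of 0.9 and on an inflation whose size is assumed and whose frequency the documents do not give. Redacted text also follows 5.3.1, so a further rule there cannot be ruled out. No change to the plan follows.

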5.3.2. Safety Data

Missing values in standard summaries of AEs, laboratory data, vital signs, and ECGs will be imputed according to CaPS.

6. ANALYSES AND SUMMARIES

6.1. Primary Endpoints

[figure not shown]
[figure not shown]
For assessment of the bioequivalence objective of the study (Periods 1 and 2), natural log transformed AUC_{inf} , AUC_{last} , AUC_{72} and C_{max} will be analyzed separately using a mixed effect model with sequence, period and treatment as fixed effects and participant within sequence as a random effect. Estimates of the adjusted mean differences (Test-Reference) and corresponding 90% confidence intervals will be obtained from the model. The adjusted mean differences and 90% confidence intervals for the differences will be exponentiated to provide estimates of the ratio of adjusted geometric means (Test/Reference) and 90% confidence intervals for the ratios. Treatment A (12.2 mg tafamidis free acid tablet) will be the Test treatment, while Treatment B (commercial 20 mg tafamidis meglumine softgel capsule) will be the Reference treatment.

Bioequivalence of the 2 formulations will be concluded if the 90% confidence intervals for the ratio of adjusted geometric means for both AUC_{inf} (if data permit, otherwise AUC_{last}) and C_{max} fall wholly within (80%, 125%).

For assessment of the food effect objective of the study (where treatment comparison occurs via fixed-sequence), natural log transformed AUC_{inf} , AUC_{last} , AUC_{72} and C_{max} will be analyzed separately using a mixed effect model with treatment as fixed effects and participant as a random effect. Estimates of the adjusted mean differences (Test-Reference) and corresponding 90% confidence intervals will be obtained from the model. The adjusted mean differences and 90% confidence intervals for the differences will be exponentiated to provide estimates of the ratio of adjusted geometric means (Test/Reference) and 90% confidence intervals for the ratios. Treatment C (12.2 mg tafamidis free acid tablet, fed) will be the Test treatment, while Treatment A (12.2 mg tafamidis free acid tablet, fasted) will be the Reference treatment.

Residuals from the models will be examined for normality and the presence of outliers via visual inspection of plots of residuals vs predicted values and normal probability plots of residuals but these will not be included in the CSR. If there are major deviations from normality or outliers then the effect of these on the conclusions will be investigated through alternative transformations and/or analyses excluding outliers. Justification for any alternative to the planned analysis will be given in the report of the study.

CCI

- CCI

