6.4.3. Blinding of the Sponsor

Sponsor staff will be unblinded to participants' assigned study intervention.

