Appendix 1. SAS Code for Analyses

An example of the PROC MIXED code is provided below:

For primary objective: Treatment A (Test) vs Treatment B (Reference)

```
proc mixed data=tab.pk;
  where trt in ("A", "B");
    class seq period trt participant;
    model l&var=seq period trt/ ddfm=KR;
    random participant(seq) /participant=participant(seq);
    lsmeans trt;
    estimate 'A vs B' trt 1 -1 /cl alpha=0.1;

    ods 'Estimates' out=est&var;
    ods 'lsmeans' out=ls&var;
    ods 'covparms' out=cov&var;
    ods 'tests3' out=tst&var;
run;

/* Letter assignments for treatments (trt) within the estimate statement above are as follows
A: 12.2 mg tafamidis free acid tablet, fasted (Test)
B: Commercial 20 mg tafamidis meglumine soft gelatin capsule, fasted (Reference) */
```

For secondary objective: Treatment C (Test) vs Treatment A (Reference)

```
proc mixed data=tab.pk;
  where trt in ("A", "C");
    class trt participant;
    model l&var=trt / ddfm=KR;
    random participant / subject=participant;
    lsmeans trt;
    estimate 'C vs A' trt -1 1 /cl alpha=0.1;

    ods 'Estimates' out=est&var;
    ods 'lsmeans' out=ls&var;
    ods 'covparms' out=cov&var;
    ods 'tests3' out=tst&var;
run;

/* Letter assignments for treatments (trt) within the estimate statement above are as follows;
A: 12.2 mg tafamidis free acid tablet, fasted (Reference)
C: 12.2 mg tafamidis free acid tablet, fed (Test) */
```

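### Does the SAP let an outlier-excluded or re-transformed analysis decide bioequivalence in place of the planned one?

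*SAP*

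**What the plan says.** SAP 5.1 sets up two one-sided hypotheses. Bioequivalence is concluded if the 90% confidence intervals for the ratios of adjusted geometric means of AUCinf (AUClast if data do not permit AUCinf) and Cmax "fall entirely within the acceptance region of (80%, 125"%). SAP 6.1 repeats the rule and names the model: natural-log parameters, with sequence, period and treatment as fixed effects and participant within sequence as random. Appendix 1 codes the contrast as "estimate 'A vs B' trt 1 -1 /cl alpha=0.1".

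The next paragraph of SAP 6.1 has residuals inspected by eye, with the plots kept out of the study report. Where there are major departures from normality or outliers, the effect on the conclusions is to be investigated through "alternative transformations and/or analyses excluding outliers. Justification for any alternative to the planned analysis will be given in the report".

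At concentration level, SAP 5.3.1 states: "Anomalous concentration values may be excluded from PK analysis at the discretion of the PK analyst". Protocol 6.4.3 adds: "Sponsor staff will be unblinded to participants' assigned study intervention".

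Two other places bear on the point. Protocol 9 lets the SAP modify the protocol's analyses but requires an amendment for major changes to the primary ones. SAP 2.1 declares no modifications to the protocol's analysis plan.

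**The concern.** The last sentence quoted from SAP 6.1 speaks of an alternative to the planned analysis, justified in the report and so after the data are known. No numerical outlier criterion is given, and staff know the treatments. Deleting the participant with the largest residual narrows the interval. With as few as 18 evaluable participants, one deletion could turn a failure into a pass.

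If bioequivalence could be claimed from whichever analysis passed, the 5% one-sided level would no longer hold. Discretion over single concentrations looks like a second route to the same end. At stake is the trial's only confirmatory conclusion.

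**Working it through.** **Inputs.** Limits ln 0.80 and ln 1.25 (SAP 5.1). Each one-sided test is at 5%, implied by alpha=0.1 in Appendix 1. Evaluable n = 18, within-participant SD 0.098 (AUCinf) and 0.119 (Cmax), true ratio 0.9 (Protocol 9.5). Residual cut-offs of 2.0, 2.5 and 3.0 are assumptions, since the SAP gives none.

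**The plan's own figures.** With complete data in Periods 1 and 2, the model reduces to sequence-adjusted within-participant differences, with SE = SD × √(2/n) and n − 2 degrees of freedom.

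- AUCinf: SE = 0.098 × √(2/18) = 0.0327; exact power 96.4%.
- Cmax: SE = 0.119 × √(2/18) = 0.0397; exact power 88.4%.
- Product: 0.964 × 0.884 = 85.2%.

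Protocol 9.5 states 97%, 89% and about 86%; the synopsis states 95%, 89% and about 85%. All lie within two points. At a true ratio of 0.80 the planned test has size 5.0%.

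**What a substitution would cost.** I simulated 200,000 two-period crossovers per setting: n = 18, SD 0.119, true ratio 0.80, normal data with no real outliers. The participant with the largest residual is dropped if that residual exceeds the cut-off. The planned analysis alone gives about 5.0%.

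| Residual type | Cut-off | Trials flagged | Trimmed replaces planned | Either may pass |
|---|---|---|---|---|
| External | 3.0 | 16% | 6.4% | 6.6% |
| External | 2.5 | 42% | 7.6% | 8.1% |
| External | 2.0 | 84% | 9.1% | 10.2% |
| Internal | 3.0 | 0.9% | 5.2% | 5.2% |
| Internal | 2.5 | 13% | 6.2% | 6.4% |
| Internal | 2.0 | 64% | 8.5% | 9.3% |

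The two residual types are linked by external = internal × √((df − 1)/(df − internal²)). With df = 16, an internal value of 2.5 becomes 2.5 × √(15/9.75) = 3.10. That is why internal 2.5 and external 3.0 give nearly the same risk. If any one participant could be dropped at will, the risk at n = 18 would be about 13.7%.

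**Per endpoint or per trial.** Both endpoints must pass. With both true ratios at 0.80 and an assumed correlation of 0.3 to 0.7 between the endpoints' differences, the planned rule gives false bioequivalence in 0.7% to 1.9% of trials. Letting either analysis pass on each endpoint gives 1.0% to 4.2% (external) or 0.7% to 3.7% (internal). The table describes the trial only when the other endpoint passes almost surely.

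**What the documents permit.** The middle clause of the SAP 6.1 sentence sets the purpose: to see what outliers do to the conclusions. That presupposes conclusions already reached from the planned model. The decision rule has no exception clause, and nothing says a claim may rest on whichever analysis passes. An analysis on another scale does not directly yield a ratio of geometric means, so it cannot be read against 80% to 125%; it can only be supportive. The substitution columns therefore price a procedure that the plan does not contain.

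**Concentrations.** SAP 5.3.1 first defines an anomalous value. Its bioanalytical validity must have been verified, and it must be grossly inconsistent with other data from that participant or from others. The analyst's discretion covers only values that meet this definition. SAP 4 has membership of the analysis sets assessed before database release. The simulation does not model concentration exclusions, so their effect is not quantified here.

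**The case for a change.** A pure sensitivity analysis is not an alternative to the planned analysis and would need no justification as one, so the last sentence of that paragraph appears to contemplate substitution. An outlier-excluded model on the log scale does give a ratio of geometric means with a 90% interval, so it could be set against the limits. Protocol 9 leaves the word major undefined. The risk at a cut-off of 3 moves from 5.2% to 6.6% on residual type alone, which argues for prespecification. One sentence saying that the planned model governs would cost almost nothing and would leave the stated power untouched.

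Part of this stands. The sentence is loose, there is no outlier criterion, and precedence is left to be inferred. But such a sentence would restate a rule that SAP 5.1 and 6.1 already give; it would alter no analysis. Making a trimmed analysis decisive would change the primary analysis, which fits neither SAP 2.1 nor, on any ordinary reading, Protocol 9 without an amendment. The 10% figure needs a cut-off that flags 84% of perfectly normal trials, hard to square with a trigger worded as major deviations or outliers.

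Limiting concentration exclusions to documented failures, settled before treatment codes are joined, is a separate matter. It presupposes a blinded stage that this open-label trial lacks, and it would keep in the primary derivation values that are plainly inconsistent but have no identified cause. That is a debatable trade-off.

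**Conclusion.** No change follows. This is a gap that analysts fill sensibly: the planned natural-log model in Periods 1 and 2 decides, and outlier-excluded or re-transformed analyses are reported beside it to show how robust the result is. On that reading the false-bioequivalence risk is 5.0% per endpoint and the stated power holds.

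The rise to about 5% to 10% per endpoint (n = 18, true ratio 0.80, normal data, at most one exclusion) depends on an either-passes rule found nowhere in the documents, on assumed cut-offs and residual type, and on a second endpoint that passes almost surely. With both endpoints at the limit, and the assumed correlations, even that rule leaves the trial-level risk at or below 4.2%. Should planned and trimmed results disagree, the decision rule already says which one counts. Text is redacted just after both SAP paragraphs, so further handling rules may exist there; this conclusion does not rely on them.
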